5.1. Summary of Study Design

Study JAHN is a Phase 3, multicenter, double-blind study to evaluate the long-term safety and efficacy of daily baricitinib 1 mg, 2 mg, and 4 mg in patients with atopic dermatitis (AD) for approximately 2 years. The study will consist of 3 study periods and 1 substudy: randomized treatment withdrawal and downtitration. Patients entering Study JAHN will be classified as “responders,” “partial responders” or “nonresponders” based on the following criteria:

- **Responders (IGA of 0 or 1):** patients entering Study JAHN who have an IGA score of 0 or 1 and were not rescued in the originating study
- **Partial Responders (IGA of 2):** patients entering Study JAHN who have an IGA score of 2 and were not rescued in the originating study
- **Nonresponders:** any patient who does not meet the “responder” or “partial responder” definitions

Figure JAHN.5.1 illustrates the study design. The full visit schedule is outlined in the Study Schedule of Activities in the Protocol. Patients who completed originating studies, such as Studies JAHL, JAHM or JAIY may be eligible for enrollment into Study JAHN. This study also includes an open-label addendum for which patients do not have to complete an originating study.

[figure not shown]
Patients completing Studies JAHL, JAHM or JAIY will have had approximately 16 weeks of treatment with investigational product (IP) (baricitinib or placebo) and will enter Study JAHN at Visit 1; the final visit of Study JAHL, JAHM or JAIY will be the first visit of Study JAHN unless washout of a concomitant medication was required in which case a new Visit 1 is required. If oral systemic AD treatments were administered for rescue in the originating study, then a minimum washout of 4 weeks is required prior to study drug initiation in Study JAHN (Visit 1). Patients will have been using emollients daily in their originating study and thus will continue during Study JAHN participation.

Daily diary dispensation/collection will continue through the first 4 months of treatment in JAHN and then dispensation will resume at Week 48 for an additional 5 months of collection to capture PROs prior to and during the withdrawal and downtitration substudy (except for patients known not to be in the substudy).

Study JAHN will consist of 4 periods:

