5.2. Method of Assignment to Treatment

At entry into Study JAHN, patients who meet all criteria for enrollment will be randomized or assigned treatment by a computer-generated random sequence using an interactive web-response system (IWRS). Patients originally assigned to placebo, 1-mg baricitinib, or 2-mg baricitinib in Studies JAHL or JAHM, or patients originally assigned to placebo or 2-mg baricitinib in Study JAIY and classified as nonresponders, will be randomized in a 1:1 ratio to 2-mg baricitinib or 4-mg baricitinib and will be stratified by disease severity at baseline of JAHN (IGA 0, 1, 2 versus IGA 3 versus IGA 4). All other patients will be assigned to treatment in Study JAHN matching their prior assignment from Studies JAHL, JAHM, or JAIY.

Additional addendum patients will be permitted to enroll directly into Study JAHN on baricitinib 2 mg. These patients will not be blinded to treatment.

At Week 52, patients eligible for the withdrawal and downtitration substudy will be assigned to treatment by a computer-generated random sequence using an IWRS. Rerandomization will follow a 1:1:1 ratio allocation and will be stratified by disease severity (IGA 0, 1 versus IGA 2). Patients entering the substudy on baricitinib 4 mg will be rerandomized to baricitinib 4 mg, baricitinib 2 mg, and placebo; patients entering the substudy on baricitinib 2 mg will be rerandomized to baricitinib 2 mg, baricitinib 1 mg, and placebo.

The IWRS will be used to assign blister packs, each containing double-blind IP tablets, to each patient, starting at Visit 1 (Week 0), and at each visit up to and including Visit 21 (Week 184). Site personnel will confirm that they have located the correct blister packs by entering a confirmation number found on the blister packs into the IWRS.

This study will be conducted internationally in multiple sites. [Table JAHN.5.1](#) describes how regions were defined for stratification in the originating studies.

Table JAHN.5.1. Geographic Regions for Stratification

Region	Country
Europe	Austria, Czech Republic, Denmark, France, Germany, Hungary, Italy, Poland, Spain, Switzerland
Japan	Japan
Rest of World	Argentina, Australia, India, Israel, Korea, Mexico, Russia, Taiwan

6. A Priori Statistical Methods

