6.1. Determination of Sample Size

It is anticipated that 95% of enrolled patients will complete Studies JAHL, JAHM, and JAIY and roll over into Study JAHN. Therefore, planned enrollment into Study JAHN from the originating Studies JAHL, JAHM, and JAIY will be approximately 1425 patients. Patients who are nonresponders at entry into Study JAHN and were not randomized to baricitinib 4 mg will be randomized 1:1 to either baricitinib 4 mg or baricitinib 2 mg and will be stratified by disease severity at baseline of JAHN (IGA 0, 1, and 2 versus IGA 3 versus IGA 4). This study is intended to evaluate patients' long-term response of baricitinib, and the sample sizes are not determined to detect differences between baricitinib and an appropriate comparator in a statistically powered manner. Additional patients may enroll from addenda or other studies.

Patients at Week 52 will be stratified by responder status (IGA 0 or 1 versus IGA 2) when entering the randomized withdrawal and downtitration substudy. It is estimated that there will be approximately 600 patients entering the randomized withdrawal and downtitration substudy. The substudy is meant to evaluate the change in clinical response after treatment withdrawal or downtitration and does not account for whether the sample size is sufficient to detect a difference between baricitinib and placebo. Maintenance of treatment benefit is defined as response of IGA 0, 1, or 2.

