6.2.3. Analysis Methods

As few placebo patients are expected to be responders, no formal comparisons between treatment groups and placebo will be conducted for the responder and partial responder mITT populations. For the nonresponder mITT population, the following comparisons will be made for Period 1:

- for patients from originating monotherapy studies:
 - baricitinib 2 mg to baricitinib 4 mg versus baricitinib 2 mg to baricitinib 2 mg
 - baricitinib 1 mg to baricitinib 4 mg versus baricitinib 1 mg to baricitinib 2 mg
 - placebo to baricitinib 4 mg versus placebo to baricitinib 2 mg
- for patients from originating combination therapy study:
 - baricitinib 2 mg to baricitinib 4 mg versus baricitinib 2 mg to baricitinib 2 mg
 - placebo to baricitinib 4 mg versus placebo to baricitinib 2 mg

For the Period 2 substudy, the following treatment comparisons will be performed:

- for patients on baricitinib 4 mg in Period 1:
 - placebo versus baricitinib 4 mg
 - baricitinib 2 mg versus baricitinib 4 mg
- for patients on baricitinib 2 mg in Period 1:
 - placebo versus baricitinib 2 mg
 - baricitinib 1 mg versus baricitinib 2 mg

For Period 1, the main analysis method of categorical efficacy variables will use a logistic regression analysis with region, baseline disease severity from originating study (IGA 3 or IGA 4), baseline value from originating study, and treatment group in the model. For Period 2, the main analysis method of categorical efficacy variables will use a logistic regression analysis but with region, baseline disease severity at Week 52, baseline value at Week 52, and treatment

group in the model. In this case, the baseline disease severity at Week 52 can take values in 1 of 2 levels: 1) IGA of 0 or 1, and 2) IGA of 2. Firth's correction will be used in order to accommodate (potential) sparse response rates. The p-value for the odds ratio from the logistic regression model will be used for statistical inference, unless Firth's correction still results in quasi-separation. In that case, a Fisher's exact test p-value will be used for statistical inference. The difference in percentages and 100(1-alpha)% CI of the difference in percentages using the Newcombe-Wilson method without continuity correction will be reported.

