For nonresponders, the main analysis method for all continuous efficacy variables will use MMRM analysis. The MMRM model will use a restricted maximum likelihood estimation. The model will include treatment, region, baseline disease severity (IGA), visit, and treatment-by-visit interaction as fixed categorical effects, and baseline and baseline-by-visit interaction as fixed continuous effects. For daily diary assessment endpoints, the model term 'visit' will include each of 16 weeks. An unstructured (co)variance structure will be used to model the between- and within-patient errors. If this analysis fails to converge, the heterogeneous autoregressive (ARH[1]), followed by the heterogeneous compound symmetry (CSH), followed by the heterogeneous Toeplitz, followed by autoregressive (AR[1]), followed by compound symmetry will be used. The Kenward-Roger method will be used to estimate the degrees of freedom. Treatment least square means (LSM) will be estimated within the framework of the MMRM using type 3 sums of squares. Differences in LSM between each dose of baricitinib and an appropriate comparator (and associated p-values, standard errors and 95% CI) will be used for statistical inference. The LSM difference, standard error, p-value, and 95% CI will be reported. For responders and partial responders, descriptive statistics will be provided for all continuous efficacy and health outcomes variables.

Treatment comparisons for select continuous efficacy and health outcomes variables may also be made using ANCOVA for primary and secondary objectives. For Period 1 analysis, when an ANCOVA model is used, the model includes region, baseline disease severity, treatment group, and baseline value. Treatment LSM will be estimated within the framework of the ANCOVA using type 3 sums of squares. Reported differences in LSM and associated p-values, standard errors, and 95% CI will be used for statistical inference. Analysis of covariance will be the primary method of analysis for continuous efficacy and health outcome variables for Period 2. In this Period, ANCOVA model includes region, baseline disease severity at Week 52, treatment group, and baseline value at Week 52. Baseline disease severity is defined previously.

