 - If year of onset is missing, duration of AD will be set as missing. Otherwise, unknown month will be taken as January, and unknown day will be taken as 01. The duration of AD will be rounded to 1 decimal place.
- duration of AD (years) category (0 to <2 years, 2 to <5 years, 5 to <10 years, 10 to <20 years, ≥20 years)
- diagnosis age (year), derived using diagnosis date as the reference start date and July 1st of birth year and truncated to a whole-integer age
- diagnosis age group (<18, ≥18 to <50, ≥50 years old)
- change from baseline = postbaseline measurement at Visit x – baseline measurement from originating study
 - If a baseline value is missing, it will not be imputed and the change from baseline will not be calculated.
- percent change from baseline at Visit x:

$$([\text{postbaseline measurement at Visit x} - \text{baseline measurement}] / \text{baseline measurement}) * 100$$
 - If a baseline value is missing, it will not be imputed and percent change from baseline will not be calculated.
- Weight (kg) = weight (lbs) * 0.454
- Weight category (<60 kg, ≥60 to <100 kg, ≥100 kg)
- Height (cm) = height (in) * 2.54
- cyclosporine inadequate efficacy prior to entry into originating study (yes, no)
 - Set to **yes** if the reason for discontinuation is inadequate response.

- cyclosporine intolerance prior to entry into originating study (yes, no)
 - Set to **yes** if the reasons for discontinuation are: intolerance to medication or contraindication (physician indicated cyclosporine was used and a contraindication was noted).
- cyclosporine contraindication (ineligible) prior to entry into originating study (yes, no)
 - Set to **yes** if cyclosporine was never used because of a contraindication.
- cyclosporine inadvisable prior to entry into originating study (yes, no)
 - Set to **yes** if the following reasons were selected for either not using the medication or discontinuing the medication:
 - reason for not using medication: physician decision, concern about side effects, unfavorable benefit risk, contraindication.
 - reasons for discontinuation: inadequate response, intolerance to medication, or contraindication.
- TCNI inadequate efficacy prior to entry into originating study (yes, no)
 - Set to **yes** if the reason for discontinuation is inadequate response.
- TCNI intolerance prior to entry into originating study (yes, no)

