6.3. Adjustments for Covariates

The randomization to treatment groups in the originating studies is stratified by disease severity (IGA) and geographic region. For Period 1, the covariates used in the logistic model for categorical data will include the baseline value from the originating study. When an MMRM analysis is performed, baseline value from originating study and baseline-by-visit interactions will be included as covariates. Unless otherwise specified, the statistical analysis models will adjust for these stratification variables. For Period 2, the covariates used in the logistic model for categorical data will include the baseline value from Week 52.

The baseline value from Study JAHN will be used as a covariate in the ANCOVA model for continuous safety data.

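### The Period 1 nonresponder model leaves out the JAHN-entry IGA strata used to randomise (a modest loss of precision), and the pooled Long-Term 4-mg population under-represents Week 52 responders by design

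*SAP*

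**What the plan says.** **Period 1 randomisation and model.** SAP Section 5.2 states that eligible nonresponders "will be randomized in a 1:1 ratio to 2-mg baricitinib or 4-mg baricitinib and will be stratified by disease severity at baseline of JAHN", with strata IGA 0-2, IGA 3 and IGA 4; Section 6.1 repeats this. The categorical model in Section 6.2.3 is a "logistic regression analysis with region, baseline disease severity from originating study (IGA 3 or IGA 4), baseline value from originating study, and treatment group". Section 6.3 describes the stratification of the originating studies and then says: "Unless otherwise specified, the statistical analysis models will adjust for these stratification variables". The mixed model in Section 6.2.3 is less specific: "The model will include treatment, region, baseline disease severity (IGA), visit, and treatment-by-visit interaction as fixed categorical effects". It does not say which study's severity is meant, and neither does the Period 1 ANCOVA. For the substudy the SAP uses the current strata: "logistic regression analysis but with region, baseline disease severity at Week 52, baseline value at Week 52, and treatment".

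**Long-Term 4-mg population.** SAP Section 6.2.1 takes patients randomised to 4 mg in an originating study who are still on 4 mg at Week 52, continue 4 mg and receive a Period 2 dose, whether or not they were eligible for the substudy. Under Section 5.2, substudy entrants on 4 mg are re-randomised 1:1:1 to 4 mg, 2 mg or placebo. Under Section 5.1, patients outside the substudy stay on their treatment. Section 4.3 and Table JAHN.6.5 plan descriptive summaries of the pool, with no weights and no split by substudy status.

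**The concern.** The covariates in the Period 1 model date from before the originating study, after which patients "will have had approximately 16 weeks of treatment with investigational product". Severity at JAHN entry, which defines the randomisation strata, is likely to predict later response better. Leaving it out costs precision and leaves chance differences in entry severity between the 2-mg and 4-mg arms uncorrected, although the data are already collected.

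In the Long-Term 4-mg pool, allocation removes about two thirds of the patients who met the substudy's IGA criterion at Week 52 and none of the others. A reader who takes the pooled curve as the long-term course of patients kept on 4 mg would see a lower response that comes partly from the 1:1:1 ratio and not from the drug.

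**Working it through.** **(a) Strata against covariates**

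1. Strata used: JAHN-entry IGA 0-2, 3, 4 (Section 5.2). Covariates used: originating IGA 3 or 4, originating baseline value, region (Section 6.2.3). The model has no counterpart to entry IGA 0-2. That stratum can be occupied, because Section 5.1 classes a patient rescued in the originating study as a nonresponder whatever the IGA. (Section 6.2.3 elsewhere describes nonresponders as IGA above 2; the two should be reconciled.)
2. Scope: Section 6.2.3 lists five nonresponder contrasts. The nonresponder rows of the current Table JAHN.6.5 name only the combination-therapy study, which has two: 2 mg to 4 mg v 2 mg to 2 mg, and placebo to 4 mg v placebo to 2 mg. For responder endpoints the logistic model is run with NRI, which Section 6.4.3 makes a sensitivity analysis from the February 2021 lock; the mLOCF rows are descriptive. The exploratory mixed model is affected only by implication of Section 6.3.
3. Arm size is not given. Assuming 1425 patients split equally over three studies and three arms, with 60-80% nonresponders: 1425/3 = 475; 475/3 × 0.6 to 0.8 / 2 = 48 to 63 per arm.
4. Simulation with the planned covariates and Firth's correction. Assumptions: conditional odds ratio 2; entry strata 10/50/40%; 2-mg response 13-29%; blocks of 4 within strata; 2000 trials in each of 24 settings. The revised model adds the entry stratum and a continuous entry value.

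| Per arm | Change in power (points) | Example |
|---|---|---|
| 50 | -0.7 to +3.7 | 16% to 20% |
| 100 | +0.4 to +6.1 | 35% to 41% |

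 Type I error as planned is 3.2-5.1%.
5. A simpler model (originating IGA and treatment only) with the strata alone added, mix 20/50/30%, odds ratio 2: at 75 per arm power goes from 45% to 49% (moderate stratum effect) or 33% to 43% (strong); at 150 per arm from 75% to 78% or 63% to 71%. Type I error moves from 2.6-4.2% to about 5%.
6. Section 5.2 does not stratify by prior treatment, so balance within one contrast is not guaranteed. With 40% at entry IGA 4, a difference of 10 points or more between arms arises in 15-26% of contrasts at 50 per arm and 4-11% at 100.

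**(b) Composition of the 4-mg pool**

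1. The plan's own figure: 250 × 0.80 × 0.30 = 60 addendum entrants (Protocol Section 4.8.1), matching the 60 in Protocol Section 4.4.
2. Let e be the share of 4-mg patients at Week 52 who enter the substudy. No 4-mg figure is given. All-dose proxies are (600 - 60)/1425 = 38%; with 80% completion, 540/(0.8 × 1425) = 47%; and the addendum's own 30%.
3. Entrant share of the pool = (e/3)/(e/3 + 1 - e): 12.5% at e = 30%, 17% at 38%, 23% at 47%.
4. With response rE in entrants kept on 4 mg and rN in non-entrants, the rate for all patients is e·rE + (1 - e)·rN. The pool gives (e·rE/3 + (1 - e)·rN)/(e/3 + 1 - e). The rates are assumed:
 - e = 0.38, 50% v 10%: all 0.190 + 0.062 = 25%; pool (0.063 + 0.062)/0.747 = 17%.
 - e = 0.38, 50% v 20%: all 0.190 + 0.124 = 31%; pool (0.063 + 0.124)/0.747 = 25%.
5. The shortfall is (2/3)·e·(1 - e)·(rE - rN)/(1 - 2e/3), which is zero when rE = rN.
6. Direction at Week 52: the re-randomisation strata are only IGA 0-1 and IGA 2 (SAP Section 5.2), and Protocol Section 4.3.1.2, which points to the main-protocol substudy, requires IGA 0-2. Non-entrants can include some IGA 0-2 patients (recent high-potency TCS, drug interrupted), which narrows the gap.

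**The case against.** For (a): the study is not powered for comparisons (Section 6.1), the affected analyses are not primary, and unadjusted percentage differences are reported anyway. All of that stands and limits the weight of the point. Three stronger readings are tempting and should be resisted.

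- A reader might infer that the omission could create a false advantage for 4 mg. It does not: treatment is randomised, and the simulated type I error is at or below nominal apart from simulation noise.
- A reader might see the smaller adjusted odds ratio (mean 1.65-1.96 as planned v 1.86-2.02 revised) as bias. It is largely non-collapsibility: the two models estimate different conditional odds ratios.
- A reader might apply the point to all five contrasts, or take it as explicit for the mixed model. The current tables and the silence on the source of severity do not support that.

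Adding the entry value of the endpoint is also nearly redundant for IGA responses, where that value is the stratifying score. Section 6.15 likewise limits its baseline-value term to EASI and itch.

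For (b): the SAP never says that the pool estimates all originating 4-mg patients; it is defined by continuing 4 mg and is exploratory. That stands, so the fault lies in how the summary can be read, and is not a breach of a stated estimand. A reader might conclude that 4-mg response is understated by a known amount. The documents give no response rates by substudy status, and censoring at retreatment or rescue (Section 6.4) and observed-only data after Week 104 (Section 4.3) could change the gap over time. Other displays help only in part. The planned 4-to-4 mg summary covers Week 52 itself, but the substudy 4-mg arm and the nonsubstudy 4-mg group are not limited to patients on 4 mg since the originating study.

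**Conclusion.** Both points hold, and both are moderate.

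(a) The explicit mismatch is in the logistic model. It costs efficiency and leaves chance imbalance uncorrected; it does not threaten validity. The size is roughly 0 to 6 points of power with the planned covariates, and 3 to 10 in the simpler model that assumes stronger stratum effects. Arm sizes, stratum mix and prognostic strength are all assumptions.

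(b) The under-representation of Week 52 responders follows from the eligibility rule and the allocation ratio. Its effect after Week 52 depends on entry share and response rates that the documents do not give, so 25% reading as 17% is an illustration and not an estimate. The pooled figure describes the patients who happened to remain on 4 mg. It should not be presented as the long-term response of all patients who started 4 mg in an originating study and reached Week 52 on it.

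**What to change.** **(a)** In Sections 6.2.3 and 6.3, add the JAHN-entry IGA stratum (0-2, 3, 4) to the Period 1 nonresponder models. Add the JAHN-entry value only for non-IGA endpoints such as EASI and itch. Leave the definition of change endpoints as in Section 6.2.4: "change from baseline = postbaseline measurement at Visit x – baseline measurement from originating study". State which study's severity the mixed model and ANCOVA use. Cost: two stratum parameters and, for some endpoints, one covariate. The 0-2 stratum may be sparse, but Firth's correction is already planned for the logistic model. If entry severity predicts weakly, a fraction of a power point may be lost.

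**(b)** Within the Long-Term 4-mg population, report substudy patients re-randomised to stay on 4 mg and non-entrants separately, beside the planned pooled summary. A figure giving stayers a weight of 3 (the inverse of 1/3) with robust confidence intervals may be shown as supplementary. Its design effect is (1 - 2e/3)(1 + 2e), or 1.28 to 1.33 for e of 30-60%. Where entrants respond better, weighting makes the 4-mg result look more favourable, so it should not replace the planned figure.

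No new data are needed. The Version 8 entry in the revision history says data to Week 104 are locked, so label both additions as made after lock and show them beside the planned results.

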6.2. General Considerations

This plan describes *a priori* statistical analyses for efficacy, health outcomes, and safety that will be performed.

Statistical analysis of this study will be the responsibility of Eli Lilly and Company (Lilly). The statistical analyses will be performed using SAS® Version 9.4 or higher.

Not all displays described in this statistical analysis plan (SAP) will necessarily be included in the clinical study report (CSR). Not all displays will necessarily be created as a “static” display. Some may be incorporated into interactive display tools instead of or in addition to a static display. Any display described in this SAP and not included in the CSR would be available upon request.

Statistical tests of treatment effects and confidence intervals (CIs) will be performed at a 2-sided significance level of 0.05, unless otherwise stated.

Data collected at early termination visits will be mapped to the closest scheduled visit if it falls within the visit window as discussed in Section 6.2.2. For by-visit summaries, only visits in which a measure was scheduled to be collected will be summarized. Any unscheduled visit data will be included at the patient-level listings. However, the data will still be used in other analyses, including categorical analyses for safety.

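### Substudy response differences through Week 104 get an unstratified Newcombe-Wilson interval beside a p-value adjusted for the Week 52 IGA stratum; the interval is conservative and can disagree with the test when that stratum is strongly prognostic

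*SAP*

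**What the plan says.** SAP Section 5.2 sets the design at Week 52: "Rerandomization will follow a 1:1:1 ratio allocation and will be stratified by disease severity (IGA 0, 1 versus IGA 2"). For Period 2 categorical endpoints, Section 6.2.3 specifies a "logistic regression analysis but with region, baseline disease severity at Week 52, baseline value at Week 52, and treatment" group, with Firth's correction. It adds that "the baseline disease severity at Week 52 can take values in 1 of 2 levels", and these are the two rerandomisation strata.

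The same paragraph names the basis for inference: "The p-value for the odds ratio from the logistic regression model will be used for statistical inference". Fisher's exact test takes over if quasi-separation remains. The paragraph then ends with the percentage scale: "The difference in percentages and 100(1-alpha)% CI of the difference in percentages using the Newcombe-Wilson method without continuity correction will be reported". The level is two-sided 0.05 (Section 6.2).

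No stratified version, weights or model-based risk difference appears there or in the Period 2 rows of Tables JAHN.6.5 and JAHN.6.7. The SAP does not use the word unstratified; that is the plain reading of the method it names.

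For Period 2 continuous endpoints, Section 6.2.3 takes the difference, its interval and the p-value from one ANCOVA adjusted for Week 52 severity. Only the categorical endpoints mix an adjusted test with an unadjusted interval.

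**The concern.** Stratified rerandomisation balances the Week 52 IGA groups between arms, so variation between the strata should not count as uncertainty in the treatment difference. A plain two-sample interval counts it anyway.

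The effect is most plausible for IGA (0,1). There, one stratum enters the substudy as responders and the other as nonresponders on the endpoint's own scale. For IGA (0,1,2) both strata enter as responders, and EASI75 is a different scale, so the stratum may matter less.

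The substudy asks how much response is lost on withdrawal or down-titration, and the percentage difference with its interval is the most readable answer. A report could print a p-value below 0.05 beside an interval that includes 0 for the same secondary endpoint.

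**Working it through.** **The plan's own figure.** Protocol Section 4.8.1 gives 250 addendum patients, 80% completing Week 52 and 30% of those entering the substudy: 250 × 0.80 × 0.30 = 60, as stated in Protocol Section 4.4. The 600 substudy entrants in SAP Section 6.1 have no stated inputs. No interval width or power is stated.

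**Assumptions.** The split of the 600 by entry dose, the stratum shares and the response rates are not given. An even split over two entry doses and three arms gives 600 / 6 = 100 per arm. Strata are taken as equal unless stated.

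**Step 1: large-sample effect.** Take stratum rates p1 and p2, the same in both arms, with mean p. The plain interval uses the variance p(1 − p). The stratified one uses the within-stratum mean [p1(1 − p1) + p2(1 − p2)] / 2. The width ratio r is the square root of the second over the first, and coverage of the plain interval is about 2Φ(1.96 / r) − 1.

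| p1 / p2 | p(1 − p) | Within-stratum mean | r | Approximate coverage |
|---|---|---|---|---|
| 70% / 20% | 0.2475 | 0.1850 | 0.865 | 97.7% |
| 80% / 10% | 0.2475 | 0.1250 | 0.711 | 99.4% |
| 60% / 30% | 0.2475 | 0.2250 | 0.953 | 96.0% |
| 85% / 65% | 0.1875 | 0.1775 | 0.973 | 95.6% |

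**Step 2: simulation of the planned interval.** With 40,000 trials per scenario at 70, 100 and 130 per arm, coverage was 97.3-97.7% at 70/20, 99.3-99.4% at 80/10 and 95.5-96.0% at 60/30. With a 20-point gap and a 15-point loss (85/65 v 70/50, 100 per arm) it was about 95.5%, and the stratified interval was about 3-4% narrower.

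**Step 3: agreement with the test.** This used 100 per arm, a true 15-point loss and Firth logistic regression adjusted for the stratum (region omitted).

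| Gap between strata | Stratified interval narrower by | p < 0.05 but planned interval includes 0 | Same, stratified interval |
|---|---|---|---|
| 0 points | 0.5% | 0.0% | 0.0% |
| 20 points | 2.5% | 0.1% | 0.0% |
| 40 points | 9% | 4.3% | 0.0% |
| 60 points | 20% | 15.9% | 0.2% |

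For a 14.5-point loss (70/20 v 53/8, 100 per arm), the planned interval excludes 0 in 57% of trials and the stratified one in 69%.

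**Step 4: one worked table, 100 per arm, 50 per stratum.** Arm A has 42/50 (IGA 0/1) and 14/50 (IGA 2), total 56/100. Arm B has 35/50 and 8/50, total 43/100. The difference is 13.0 points.

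- Planned interval: the Wilson limits are 46.2 to 65.3% and 33.7 to 52.8%. Lower limit: 13.0 − √[(56 − 46.2)² + (52.8 − 43)²] = −0.8. Upper limit: 13.0 + √[(65.3 − 56)² + (43 − 33.7)²] = 26.2 (unrounded limits used). It includes 0.
- Stratified, within-stratum variance: 0.25 × (0.84×0.16 + 0.28×0.72 + 0.70×0.30 + 0.16×0.84) / 50 = 0.003402. The standard error is 0.0583, and 13.0 ± 1.96 × 5.83 gives 1.6 to 24.4. It excludes 0.
- Stratified, combining within-stratum Wilson distances: 1.3 to 24.0. It excludes 0.
- A stratified Newcombe form that recomputes a binomial variance from pooled stratified limits: −0.9 to 26.3, no gain.
- Firth model adjusted for the stratum: odds ratio 2.11, Wald p = 0.032.

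The planned test and the planned interval disagree here. The two intervals built from within-stratum variation agree with the test.

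**The case against.** The strongest reply is that the plan already says which result governs. Inference rests on the odds-ratio p-value and the interval is only reported. A reader might infer that the substudy's type I error is wrong, or that the plan leaves two rival answers. The documents support neither: no test is made from the interval, Section 6.1 sets no power target and Section 6.6 makes no multiplicity adjustment. The error is also conservative, with coverage at or above about 95% in the scenarios of 70 to 130 per arm. This reply stands and limits the point to precision and consistency.

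The size depends on assumed rates, and disagreement is most common at moderate losses. With a 25-point loss (70/20 v 35/5, 100 per arm) the planned interval excludes 0 in 98.3% of trials against 99.1% stratified, and disagreement falls to 0.8% (Cochran-Mantel-Haenszel as the adjusted test). This also stands.

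A stratified interval aligns only partly with the test. The model also adjusts for region and the Week 52 baseline value, and it concerns a conditional odds ratio, so occasional disagreement would remain. With very small arms, such as 60 / 3 = 20 per arm for addendum patients alone, the stratified interval is not reliably better.

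Finally, the SAP Version 8 entry in the revision history says that data to Week 104, including primary and secondary endpoints, are locked. Replacing a reported interval with a narrower one now would be a post-lock change. That decides the form of the fix; the mismatch itself remains.

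**Conclusion.** The point holds for the all-entrants substudy analyses through Week 104. The plan adjusts the test for the randomisation stratum and leaves the stratum out of the interval. The planned interval is valid but conservative.

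Under assumed rates of 70% and 20%, coverage is about 97.5% and a stratified interval is about 13% narrower. With a 20-point gap, as may hold for IGA (0,1,2) or EASI75, coverage is about 95.5% and the gain about 3-4%. If Week 52 IGA is not prognostic, the gain is negligible (0.5% at 100 per arm). It would therefore be wrong to call the interval too wide for every endpoint; IGA (0,1) is the plausible case for a material effect.

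The point does not reach three places: the parallel analysis of patients with Week 52 IGA 0 or 1, which is a single stratum; any analysis that falls back to Fisher's exact test, which is itself unstratified; and summaries beyond Week 104, which are descriptive on observed data unless otherwise stated (Table JAHN.6.5, footnote c).

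**What to change.** For the full Randomized Downtitration Withdrawal Substudy Population, through Week 104, add one of these to Section 6.2.3:

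- a Mantel-Haenszel-weighted risk difference over the two Week 52 IGA strata, with an interval built from within-stratum variances, for example by combining within-stratum Wilson distances; or
- a standardised risk difference, with its interval, from the same logistic model.

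Write the formula into the SAP. The name stratified Newcombe is not enough, because one version under that name gives no gain.

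Keep the plain interval for the Week 52 IGA 0/1 subset and wherever the Fisher fallback is used. Present the new interval beside the planned one, labelled as added after lock.

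The cost is a short SAP addition and one re-run, with no new data. The weighted difference will be close to the crude one because allocation is balanced within strata.
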